18. SECONDARY OUTCOMES

18.1. PART A

The following secondary efficacy parameters will be evaluated in **Part A after 3 and 6 cycles of treatment** (i.e. at the end of Cycles 3 and 6, respectively) based on ITT analysis set and PP analysis set:

- Preliminary efficacy of Givinostat (secondary endpoint) for PV/ET and MF patients, respectively:
 - **For PV and ET (if any):** CR and PR rate according to the clinico-haematological ELN response criteria [\[1\]](#);
 - **For MF (if any):** CR, major response, moderate response and minor response rate according to the EUMNET response criteria [\[7\]](#).

In all cases, the medical judgment of the Investigator's is taken into account. In particular, if the Investigator's clinical response assessment – that takes into account the overall medical judgment of the specific patient's case - is not in agreement with the exact application of the clinico-haematological ELN or EUMNET response criteria , the Investigator's assessment will supersede the "mathematical"

Document PPD

Author: PPD

Version Number:

V2.2

Version Date:

21 March 2018

Template No: CS_TP_BS016 – Revision 3

Reference: CS_WI_BS005

Effective Date: 01May2012

Copyright © 2012 Quintiles Transnational Corp. All rights reserved.

The contents of this document are confidential and proprietary to Quintiles Transnational Corp. Unauthorized use, disclosure or reproduction is strictly prohibited.

application of these criteria and used for analysis into study report. Also mathematical application of ELN response criteria (not agreed by the medical site team) will be analyzed.

Note that only in case the enrolment in **Part A** is slow (i.e. < 5 patients enrolled in 3 months, the eligibility for this part of the study can be expanded to all patients with cMPN.

Frequency and percentage of patients in each response category (CR, PR, NR rate for PV and ET; CR, major response, moderate response, minor response and NR rate for MF) will be presented at C3D28 and at Cycle 6 Day 28 (C6D28).

Of note, patients who dropped the study due to drug-related TEAE(s) before that the post-baseline efficacy measurement is obtained (i.e. at C3D28 and/or at C6D28), the post-baseline efficacy measurements (i.e. at C3D28 and/or at C6D28) will be considered as “No Response*”, even if these assessments were not performed. “*” will allow to distinguish them from them from the therapeutic response evaluation result of “No Response”, that will be reported without “*” (i.e. “No Response”). Other missing data will not be replaced, if not otherwise specified.

The following secondary parameter will be evaluated in **Part A** based on PK analysis set:

- Individual Givinostat concentrations tabulated by DL along with descriptive statistics.

Plasma concentrations from **Part A** will be listed and tabulated by dose and time point for all patients and time points with at least 1 PK assessment.

Descriptive statistics for all PK parameters for **Part A** will be calculated.

18.2. PART B

The following secondary efficacy parameter will be evaluated in **Part B after 6 cycles of treatment** (i.e. at C6D28) based on ITT analysis set and PP analysis set:

- Preliminary effectiveness of Givinostat (secondary endpoint) after 6 cycles of treatment in **Part B** for PV/ET and MF patients, respectively:
 - **For PV and ET (if any):** CR and PR rate according to the clinico-haematological ELN response criteria [1];
 - **For MF (if any):** CR, major response, moderate response and minor response rate according to the EUMNET response criteria [7].

In all cases, the medical judgment of the Investigator’s is taken into account. In particular, if the Investigator’s clinical response assessment – that takes into account the overall medical judgment of the specific patient’s case - is not in agreement with the exact application of the clinico-haematological ELN or EUMNET response criteria , the Investigator’s assessment will supersede the “mathematical” application of these criteria and used for analysis into study report. Also mathematical application of ELN response criteria (not agreed by the medical site team) will be analyzed. Note that only in case the

Document PPD

Author: PPD

Version Number:

V2.2

Version Date:

21 March 2018

Template No: CS_TP_BS016 – Revision 3

Reference: CS_WI_BS005

Effective Date: 01May2012

Copyright © 2012 Quintiles Transnational Corp. All rights reserved.

The contents of this document are confidential and proprietary to Quintiles Transnational Corp. Unauthorized use, disclosure or reproduction is strictly prohibited.

enrolment in **Part A** is slow (i.e. < 5 patients enrolled in 3 months), the eligibility for this part of the study can be expanded to all patients with cMPN.

Frequency and percentage of patients in each response category (CR, PR and NR rate for PV and ET; CCR, major response, moderate response, minor response and NR rate for MF) will be presented at C6D28. Of note, patients who dropped the study due to drug-related TEAE(s) before that the post-baseline efficacy measurement is obtained (i.e. at C3D28 and/or at C6D28), the post-baseline efficacy measurements (i.e. at C3D28 and/or at C6D28) will be considered as “No Response*”, even if these assessments were not performed. “*” will allow to distinguish them from them from the therapeutic response evaluation result of “No Response”, that will be reported without “*” (i.e. “No Response”). Other missing data will not be replaced, if not otherwise specified.

The following secondary safety parameter will be evaluated in **Part B after 6 cycles of treatment** (i.e. at C6D28, or including data related to Cycle 4 Day 28 (C4D28), Cycle 5 Day 28 (C5D28) and any unscheduled visit included in that interval period) based on SAF analysis set:

- Number of patients experiencing AEs.
- Type, incidence, and severity of treatment-related AEs, graded according to CTCAE v. 4.03 (14th June 2010).

AEs will be coded using MedDRA dictionary (using the 20.1 version). AEs will be reported on a per patient basis. If a patient has more than one AE for a treatment that coded to the same PT, the patient will be counted only once for that PT. Similarly, if a patient has more than one AE for a treatment within a SOC category, the patient will be counted only once in that SOC category. A patient with multiple CTCAE grades for an AE will be summarised under the maximum CTCAE grade recorded for the event.

Any AE which started at or after the first administration of study treatment will be considered a TEAE. If the start date is missing for an AE, the AE will be considered to be a TEAE.

TEAE included in this analysis are defined as those starting after the date of the first administration of Cycle 4.

An overview of AEs including the number of patients with at least one AE, at least one TEAE, at least one drug-related TEAE, at least one TESAE, any SAE, any AE leading to death, any TEAE leading to death, any TEAE leading to drug discontinuation, at least one grade ≥ 3 TEAE, will be presented. The following AE frequency tables will be also provided:

- Incidence of TEAEs by primary SOC and PT;
- Incidence of drug-related TEAEs by primary SOC and PT;
- Incidence of TEAEs by maximum severity, primary SOC and PT;
- Incidence of TEAEs by strongest relationship, maximum severity, primary SOC and PT;
- Incidence of TESAEs by primary SOC and PT;
- Incidence of TEAEs leading to study drug discontinuation by primary SOC and PT;

Document: PPD

Author: PPD

Version Number:

V2.2

Version Date:

21 March 2018

Template No: CS_TP_BS016 – Revision 3

Reference: CS_WI_BS005

Effective Date: 01May2012

Copyright © 2012 Quintiles Transnational Corp. All rights reserved.

The contents of this document are confidential and proprietary to Quintiles Transnational Corp. Unauthorized use, disclosure or reproduction is strictly prohibited.

- Incidence of TEAEs leading to dose modification by primary SOC and PT.

These secondary safety parameters will be evaluated in **Part B after 6 cycles of treatment** (i.e. at C6D28, or including data related to C4D28, C5D28 and any unscheduled visit included in that interval period) based on SAF analysis set and taking into account the same rules describes in the paragraphs [17.1](#).

The following secondary parameters will be evaluated in **Part B** based on PK analysis set:

- Individual Givinostat concentrations tabulated with descriptive statistics: plasma concentrations from **Part B** will be listed and tabulated by time point for all patients and time points with at least 1 PK assessment; descriptive statistics for all PK parameters for **Part B** will also be calculated; these tables will include number of observations, mean, standard deviation, median, minimum and maximum and additionally the geometric mean and Coefficient of Variation (CV), not for time to maximum plasma concentration.

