2.2. SECONDARY OBJECTIVES

PART A

- To evaluate the preliminary efficacy of Givinostat after 3 and 6 cycles of treatment according to the clinico-haematological ELN response criteria [\[1\]](#).
- To characterize PK.

PART B

- To evaluate the preliminary efficacy of Givinostat at the MTD after 6 cycles according to the clinico-haematological ELN response criteria [\[1\]](#).
- To determine the safety and tolerability of Givinostat at the MTD after 6 cycles.
- To characterize PK.

Document: PPD

Author: PPD

Version Number:

V2.2

Version Date:

21 March 2018

Template No: CS_TP_BS016 – Revision 3

Reference: CS_WI_BS005

Effective Date: 01May2012

Copyright © 2012 Quintiles Transnational Corp. All rights reserved.

The contents of this document are confidential and proprietary to Quintiles Transnational Corp. Unauthorized use, disclosure or reproduction is strictly prohibited.

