5.1. SAFETY ANALYSIS SET (SAF)

The Safety analysis set will include all enrolled patients who receive at least one dose of study medication. All safety analyses will be conducted on this population.

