Frequency and percentage of patients in each response category (CR, PR, no response (NR) for PV and ET; CR, major response, moderate response, minor response and NR rate for MF) will be presented at Cycle 3 Day 28 (C3D28). Of note, patients who dropped the study due to drug-related TEAE(s) before that the post-baseline efficacy measurement is obtained (i.e. at C3D28 and/or at C6D28), the post-baseline efficacy measurements (i.e. at C3D28 and/or at C6D28) will be considered as "No Response*", even if these assessments were not performed. "*" will allow to distinguish them from them from the therapeutic response evaluation result of "No Response", that will be reported without "*" (i.e. "No Response"). Other missing data will not be replaced, if not otherwise specified.

For **Part B** – Stage 1, Simon's design hypothesis will be evaluated by calculating the frequency and 95% CI of patients with a CR and/or PR at C3D28.

For Part B – Stage 2, the efficacy of Givinostat will be evaluated by means of a generalized linear model (logit link function and binomial distribution) adjusting for age, sex and disease type (PV, ET, MF). The therapeutic response will be collapsed in two categories in order to improve the model performance:

- For PV and ET:
 - a) "Responders" (i.e. CR and PR), and
 - b) "Not Responders" (i.e. NR);
- For MF:
 - a) "Responders" (i.e. CR, major response, moderate response and minor response), and
 - b) "Not Responders" (i.e. NR for MF).

In addition, the following primary safety parameters will be evaluated in **Part B after 3 cycles of treatment** (i.e. at the end of Cycles 3, or including data related to Cycles 1, 2 and 3) based on SAF analysis set:

- Number of patients experiencing AEs.
- Type, incidence, and severity of treatment-related AEs, graded according to CTCAE v. 4.03 (14th June 2010).

AEs will be coded using MedDRA dictionary (using the 20.1 version). AEs will be reported on a per patient basis. If a patient has more than one AE for a treatment that is coded to the same PT, the patient will be counted only once for that PT. Similarly, if a patient has more than one AE for a treatment within a SOC category, the patient will be counted only once in that SOC category. A patient with multiple CTCAE grades for an AE will be summarised under the maximum CTCAE grade recorded for the event.

Document: PPD

Author: PPD

Version Number:

V2.2

Version Date:

21 March 2018

Template No: CS_TP_BS016 – Revision 3

Reference: CS_WI_BS005

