- For titles and column labels, capitalize important words, i.e. nouns, pronouns, verbs, adverbs and adjectives but not articles, conjunctions or prepositions.
- All Footnotes will be in sentence case format.
- All symbols used in body of outputs will be footnoted.
- Continuous Variables:
 - Number (“n”),
 - Mean,
 - Standard Deviation (“SD”),
 - Median,
 - Minimum (“min”),
 - Maximum (“max”)

will be presented for all variables on the original scale.

- Categorical Variables:
 - Number (“n”),
 - Percentage (%)

in each category will be the default summary presentation.

- The percentage of patients in each category relative to the total number of patients in the relevant analysis population will be the default. Percentages relative to the total number of patients in the relevant analysis population with a non-missing assessment will be specified in a programming note on the shell if required.
- Where percentages are presented, a footnote will be added to explain what the denominator of the percentage is, in the form “Percentages are calculated relative to the total number of patients in the SAF” as the first footnote.
- All computed percentages will be presented using one decimal place except for where the percentage is 100 where no decimal places are presented.
- The percentage will be also presented if the count is zero.

Document: PPD

Author: PPD

Version Number:

V2.2

Version Date:

21 March 2018

Template No: CS_TP_BS016 – Revision 3

Reference: CS_WI_BS005

Effective Date: 01May2012

Copyright © 2012 Quintiles Transnational Corp. All rights reserved.

The contents of this document are confidential and proprietary to Quintiles Transnational Corp. Unauthorized use, disclosure or reproduction is strictly prohibited.

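### The Part B safety analysis labelled as after 6 cycles (SAP 18.2) counts only TEAEs starting after the first Cycle 4 dose date, and the SAP text describes no cumulative Cycle 1–6 table

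*SAP*

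**What the plan says.** Section 2.2 sets the Part B secondary safety objective: "To determine the safety and tolerability of Givinostat at the MTD after 6 cycles". Section 18.2 is the analysis for it. That section first gives the ordinary rule, that an adverse event with onset on or after the first study dose is treatment-emergent. It then narrows the rule for this analysis: "TEAE included in this analysis are defined as those starting after the date of the first administration of Cycle 4". The data are those of the Cycle 4, 5 and 6 visits "and any unscheduled visit included in that interval period) based on SAF analysis set".

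The primary Part B safety analysis in section 17.2 is described as "at the end of Cycles 3, or including data related to Cycles 1, 2 and 3", also on the Safety set. Both sections ask for the same overview and the same seven frequency tables, and both count a patient once per preferred term and once per system organ class.

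On the denominator, section 5.1 says: "The Safety analysis set will include all enrolled patients who receive at least one dose of study medication". Appendix 1 adds: "The percentage of patients in each category relative to the total number of patients in the relevant analysis population will be the default". A shell may instead use patients with a non-missing assessment, and a footnote must state the denominator.

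**The concern.** A reader who opens a table presented as safety after six cycles expects everything that happened from the first dose to week 24. Under section 18.2 that table leaves out every event with onset in Cycles 1 to 3. The named secondary objective would then be answered by a table that does not measure it.

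Two smaller questions follow from the same rule. Patients who stopped before Cycle 4 may sit in the denominator of a window in which they were never treated. The date that separates the two windows also has to belong to one of them.

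**Working it through.** The SAP gives no adverse-event incidence and no attrition rate, so it has no figure of its own to reproduce on this point. The only number taken from it is the Part B total of 28 (sections 3.5 and 4). The Simon design figures attached to that total do reproduce by exact binomial calculation (early termination 0.613, expected size 18.2, type I error 0.081, power 0.902), but they do not bear on safety reporting.

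**Step 1: the two windows side by side.**

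| | Section 17.2 (primary) | Section 18.2 (secondary) |
|---|---|---|
| Label | after 3 cycles | after 6 cycles |
| Onset window | Cycles 1–3, no closing date given | after the date of the first Cycle 4 dose |
| Population | Safety set | Safety set |
| Output | overview and seven frequency tables | the same |

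Section 20 adds laboratory, ECG, spleen, vital-sign and physical-examination summaries, but no adverse-event table. The SAP text therefore describes no Part B table for Cycles 1–6.

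**Step 2: can the cumulative figure be rebuilt from the two tables?** Let a be the number of patients with a given event starting in Cycles 1–3, b the number with one starting in Cycles 4–6, and N = 28. Each patient counts once per term within a table, and the overlap between tables is not shown. All that follows for the cumulative count C is

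max(a, b) ≤ C ≤ min(N, a + b).

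The values of a and b below are illustrative.

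| a | b | C | Cumulative % | Shown in the table labelled six-cycle (b/28) |
|---|---|---|---|---|
| 10 | 5 | 10 to 15 | 35.7 to 53.6 | 17.9% |
| 14 | 7 | 14 to 21 | 50.0 to 75.0 | 25.0% |
| 20 | 10 | 20 to 28 | 71.4 to 100 | 35.7% |

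The cumulative incidence is not identified, and in each example the printed figure lies below the whole possible range.

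**Step 3: the denominator.** Let d patients stop before Cycle 4 and k patients have a late-onset event. The default percentage is k/28; among those who started Cycle 4 it is k/(28 − d). The ratio of the first to the second is (28 − d)/28, so the relative understatement is d/28. The values of d are assumptions. The SAP foresees such dropouts (sections 5.2 and 22) but gives no rate. With k = 10:

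| d | Default % | % of those starting Cycle 4 | Factor | Relative understatement |
|---|---|---|---|---|
| 0 | 35.7 | 35.7 | 1.00 | 0% |
| 2 | 35.7 | 38.5 | 0.93 | 7% |
| 4 | 35.7 | 41.7 | 0.86 | 14% |
| 6 | 35.7 | 45.5 | 0.79 | 21% |
| 8 | 35.7 | 50.0 | 0.71 | 29% |

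**Step 4: the boundary.** Section 18.2 requires onset after the date of the first Cycle 4 dose, so onset on that date is outside the later window. Section 17.2 gives no closing date, so the text does not say whether the earlier window takes it.

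**The case against.** The strongest reply is that nothing is lost. Events in Cycles 1–3 are the primary Part B safety analysis, with the same set of tables, including events leading to discontinuation. Disposition with reasons for discontinuation (section 9), the listings, and the narratives for serious events, deaths and discontinuations (section 17.1) carry no Cycle 4 limit. A cumulative table can be run from patient-level data at any time. This is right, and it limits the harm to a reader who takes the later table at its label. It does not make the label correct.

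Four stronger readings are tempting and not supported:

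- A reader might infer that no 24-week table will exist. Section 8 leaves the format and content of the tables to templates that are not shown. The supportable statement is that the SAP text describes none.
- A reader might say that late incidence is understated without condition. It is not if nobody stops before Cycle 4. An all-treated denominator is also a recognised choice, and Appendix 1 requires it to be footnoted.
- A reader might say that an event on the Cycle 4 first-dose date falls in neither window. Only its exclusion from the later one is stated.
- A reader might attach one dramatic figure. Assume 60% with an early event, 20% late onset among those still treated, and 10% stopping before Cycle 4. The late table then shows 0.20 × 0.90 = 18%, against a cumulative 0.60 + 0.40 × 0.90 × 0.20 = 67%. Those rates are invented, the sum treats dropout and late onset as unrelated to early events, and most of the gap is the 60% that the primary tables already show.

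**Conclusion.** The point stands as a mismatch between an objective and its analysis. Section 18.2 presents as a six-cycle result what is by its own rule an onset-in-Cycles-4-to-6 result. The SAP text describes no table from which the Cycle 1–6 incidence can be read or derived. In the 14-and-7 example that incidence is anywhere from 50% to 75% against a printed 25%; those counts are illustrative.

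The denominator effect is conditional and secondary: d/28 in relative terms, zero without attrition before Cycle 4. It assumes 28 patients in the Part B Safety set and the Appendix 1 default. The boundary date is unassigned rather than demonstrably lost.

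This is a should-fix. The analysis is descriptive, no test, stopping rule or sample size depends on it, and early events are reported elsewhere.

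**What to change.** In section 18.2, define the six-cycle safety analysis as all TEAEs from the first dose through Cycle 6 or the end-of-study visit, on the Safety set, and remove the Cycle 4 restriction from it.

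If the late-onset table is kept, label it *onset in Cycles 4–6*, include events starting on or after the date of the first Cycle 4 dose, and show the number of patients who received a Cycle 4 dose as the denominator. Close the section 17.2 window on the day before that date, so that every event belongs to exactly one window.

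The cost is SAP wording and a re-run of standard adverse-event tables. No new data are needed.

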In **Part B**, the lowest dosage of Givinostat that can be dispensed to the patients is 50 mg b.i.d., while the highest dosage of Givinostat that could be dispensed to the patients is 100 mg b.i.d. In all the possible dosages (i.e. 50 mg b.i.d., 75 mg b.i.d., 100 mg b.i.d.), patients should self-administer daily Givinostat capsules at home at morning and in the evening (i.e. after 12 hours) with fluids and between meals (i.e. to take the study drug at least 2 two hours after the last meal, or no less than 1 hour before the meal).

Dose adjustments are permitted for patients who do not tolerate the Study protocol-specified dosing schedule, in order to allow to these patients to continue the treatment with Givinostat. The guidelines described in the Study protocol (see [paragraph 4.3.3.2.1](#) and [paragraph 4.3.3.2.2](#) of the Study protocol version 3.0) need to be followed. The objective of the Givinostat dose adjustment rules are to optimize the response for each individual patient, avoiding specific drug-related toxicities. Therefore, dose reductions or interruptions are mandated for specific toxicities and dose increases after an initial dose reduction are allowed in the case of inadequate efficacy at the reduced dosage.

Each dose modification is to be recorded on the Case Report Form (CRF).

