16.5. CRITERIA FOR CHARACTERIZATION OF PK

Plasma concentrations from **Parts A** and **B** are evaluated by dose and time point for all patients and time points with at least one PK assessment.

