Accumulation ratios Ro on Cmax, AUClast and if data permit on AUC(0- τ) will be calculated as the ratio between the individual parameter obtained on Day 28 to the corresponding one on Day 1. Ratios between metabolites (ITF-2374 and ITF-2375) to parent drug will be performed on Cmax and AUClast on day 1 and day 28.

Descriptive statistics of plasma concentrations and pharmacokinetic parameters of Givinostat will include N, Mean, SD, Coefficient of Variation (CV) Median, Minimum, and Maximum.

The following units will be used for individual and mean parameters of the compound:

- Cmax, Clast, C τ : ng/mL,
- Tmax, Tlast: hr,
- AUCs: ng·hr/mL.

Descriptive statistics of plasma concentrations and pharmacokinetic parameters of Givinostat will include N, Arithmetic Mean, SD, Geometric Mean, Coefficient of Variation (%), Min, Median and Max.

Document: PPD

Author: PPD

Version Number:

V2.2

Version Date:

21 March 2018

Template No: CS_TP_BS016 – Revision 3

Reference: CS_WI_BS005

Effective Date: 01May2012

Copyright © 2012 Quintiles Transnational Corp. All rights reserved.

The contents of this document are confidential and proprietary to Quintiles Transnational Corp. Unauthorized use, disclosure or reproduction is strictly prohibited.

Appropriate statistical methods will be applied to analyze accumulation ratio (R0) and dose proportionality.

In particular, to estimate the extent of accumulation after repeat dosing, the observed accumulation ratio will be determined using Cmax and AUClast and if data permit AUC(0- τ) log-transformed values.

A mixed effect model will be implemented with day as fixed effect and patient as a random effect. Day 28 will be compared vs Day 1 for each dose level. Again, the 90% CIs for the differences will be calculated and back-transformed.

Due to the scheme in dose escalation and the study design (parallel groups), the dose proportionality evaluation will be approached with a pure explorative intent. AUClast, Cmax and if the data permit AUC(0- τ) following repeat doses will be used for a preliminary assessment being aware the results should be interpreted with caution. The method foresees to apply the power model approach where the slope of the line obtained by regressing log(PK parameter) on log(dose) will be estimated and presented together with its 90% CI. Dose-proportionality implies a CI of regression coefficient (b as below) including 1 in the following model:

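### SAP 16.5 and 18.2 disagree on whether Part B PK is tabulated by dose, and the accumulation ratio in 18.3 has no rule for patients whose dose changed

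*SAP*

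**What the plan says.** Three sections set the PK tabulation. Section 16.5, covering Parts A and B together, says that plasma concentrations "are evaluated by dose and time point for all patients and time points with at least one PK assessment". Section 18.1 carries this out for Part A: concentrations "will be listed and tabulated by dose and time point for all patients and time points with at least 1 PK assessment". Section 18.2 has the parallel sentence for Part B without the dose: concentrations "will be listed and tabulated by time point for all patients and time points with at least 1 PK assessment".

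Section 3.4.1 starts Part B patients at 100 mg b.i.d. For Part B it says that "the lowest dosage of Givinostat that can be dispensed to the patients is 50 mg b.i.d", names 75 mg b.i.d. as a third possible dosage, caps the dose at 100 mg b.i.d., mandates reductions or interruptions for specific toxicities, and allows later increases after a reduction.

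Section 18.3 applies to both parts. Accumulation ratios "will be calculated as the ratio between the individual parameter obtained on Day 28 to the corresponding one on Day 1". For the model-based estimate, "A mixed effect model will be implemented with day as fixed effect and patient as a random effect", and "Day 28 will be compared vs Day 1 for each dose level".

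**The concern.** Characterising PK is a Part B secondary objective (Section 2.2). If Part B is summarised by time point alone, a Day 28 mean can mix doses that differ two-fold. It then describes no dose that was actually given, and a fall over cycles cannot be told apart from dose reduction. The same applies to Ro: a patient on 100 mg b.i.d. on Day 1 and on a reduced dose on Day 28 contributes a ratio that combines accumulation with the dose change.

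Part A has a safeguard here, because Section 23 rules out dose modification in its Cycle 1. The SAP states no equivalent for Part B.

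**Working it through.** The SAP states no PK figure, so there is nothing to reproduce. The check has two steps: what the text fixes, and how large the effect could be.

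**Step 1. Does the per-dose-level wording in 18.3 settle the matter?**

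- Elsewhere in the SAP a dose level is an assigned cohort. The output labels in Table 1.1 and Appendix 1 are DL1, DL1 expanded, DL6 and DL0, and the level is built into the patient ID at enrolment (Sections 3.1 and 3.4.2).
- 75 mg b.i.d. has no dose-level label.
- Part B is handled as one group elsewhere: Section 6.3 works within the MTD for Part B, and Sections 20.1, 20.3 and 23 present by dose level for Part A only.
- If dose level means assigned dose, all Part B patients fall in one level and the contrast pools them. If it means actual dose, a patient whose dose changed between the two days belongs to no single level, and no rule says how to class that patient.
- The model has terms for day and patient only.
- Section 5.2 has an actual-dose rule, but it is written for efficacy analyses.

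**Step 2. Size.**

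Inputs from the SAP: starting dose 100 mg b.i.d.; reduced dose d = 75 or 50 mg b.i.d. (Section 3.4.1); exposure proportional to dose^b (the power model of Section 18.3).

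Assumed, because the SAP does not give them: the share f of sampled patients reduced before the Day 28 sample used, and b = 1.

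For one reduced patient, Day 28 over Day 1 is multiplied by (d/100)^b. At b = 1 that is 0.75 or 0.50. Across patients, the pooled geometric mean of Ro, or of Day 28 exposure, is multiplied by (d/100)^(b·f):

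- f = 0: 1.00 for either dose
- f = 10%: 0.75^0.10 = 0.97; 0.50^0.10 = 0.93
- f = 25%: 0.75^0.25 = 0.93; 0.50^0.25 = 0.84
- f = 40%: 0.75^0.40 = 0.89; 0.50^0.40 = 0.76

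The pooled arithmetic mean of Day 28 exposure is multiplied by 1 − f + f·(d/100)^b. At b = 1 and f = 10% this gives 0.975 (75 mg) or 0.95 (50 mg). At f = 40% it gives 1 − 0.40 + 0.40 × 0.75 = 0.90, or 1 − 0.40 + 0.40 × 0.50 = 0.80.

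Sensitivity to b at f = 30%: as b goes from 0.8 to 1.2, the geometric factor goes from 0.93 to 0.90 (75 mg) and from 0.85 to 0.78 (50 mg).

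Part B starts at its maximum dose, so a dose change can only lower the Day 28 dose relative to Day 1. The effect therefore runs one way as long as exposure rises with dose.

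**The case against.** A reader might infer that the plan ignores dose in Part B PK altogether. The text does not support that. Section 16.5 names dose for both parts, Section 18.3 makes the Day 28 comparison per dose level, and Section 18.2 is silent on dose rather than ordering doses to be pooled. Pooling is one reading of inconsistent text. That part of the objection stands.

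A reader might also infer that Part B exposure and accumulation are understated as a matter of fact. That does not follow either. It needs reductions before the sample used, and the SAP does not say which cycle's Day 28 enters Ro. If it is Cycle 1, only reductions in the first four weeks count. The mention of PK samples at Cycles 3 and 6 comes from the deviation list in Section 5.3.1, which names no study part there. The detailed sampling and dose-modification rules are left to protocol paragraphs 4.5.3.2 and 4.3.3.2, and they could narrow the problem.

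It can also be said that the impact is limited. Part B PK is descriptive, no decision hangs on it, and individual concentrations and dated dose changes are both listed (Sections 18.2 and 23), so dose at sampling can be recovered. This lowers the stakes but leaves the summary tables and Ro undefined for patients whose dose changed.

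Finally, tabulating by actual dose has a bias of its own. If the patients reduced for toxicity tend to be those with high exposure, those still on 100 mg b.i.d. later are selected. That is correct and belongs with the interpretation of the table.

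**Conclusion.** The point holds as an inconsistency plus a missing rule. Sections 16.5 and 18.2 conflict on whether Part B concentrations are tabulated by dose. Section 18.3 computes Ro with no same-dose condition or normalisation, and its dose level is not defined as assigned or actual. Followed as written, Ro is confounded with dose for every patient reduced between the two days.

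The consequence is conditional. With 10% to 40% of patients reduced and dose-proportional exposure, pooled geometric mean Day 28 exposure and Ro, read as those of 100 mg b.i.d., are 7% to 24% too low if the reductions are to 50 mg b.i.d. and 3% to 11% too low if to 75 mg b.i.d. With none reduced there is no bias. The reduction shares and b = 1 are assumptions, so these figures give a range and not an estimate. The point should be corrected before the Part B PK tables are produced; it does not touch the primary efficacy analysis.

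**What to change.** In Section 18.2, tabulate Part B concentrations and PK parameters by actual dose at sampling and by time point, in line with Section 16.5. Show any table pooled over doses in dose-normalised form.

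In Section 18.3, define dose level for the PK analysis and state which cycle's Day 28 is used. Compute Ro and the Day 28 versus Day 1 model either on dose-normalised Cmax and AUC, or only in patients on the same actual dose on both days, with the excluded patients listed.

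Normalising keeps every patient but assumes proportionality, which Section 18.3 treats as exploratory. If b is really 0.8 or 1.2, the residual factor at f = 30% and 50 mg b.i.d. is 0.50^(−0.06) = 1.04 or 0.50^(0.06) = 0.96, much closer to 1 than the unnormalised 0.85 or 0.78.

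The cost is SAP wording and a dose column. Dose changes are already recorded with dates and single dose in mg (Section 23), so no new data are needed. The drawbacks are small cells at reduced doses and the selected group remaining on 100 mg b.i.d. at later time points, which should be footnoted.
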